6.2 Secondary Objectives

The secondary objectives are to assess the proof of concept (efficacy) of:

- KSL-W (30 mg dose) delivered in a chewing gum formulation compared to a placebo formulation in the change in plaque regrowth from baseline based on the QHT
- KSL-W (30 mg) in change in plaque regrowth based on sub-scores from specific regions of the upper jaw, lower jaw, buccal and lingual surface based on the QHT.

7 Trial Design

7.1 Study Measurements (Endpoints)

The primary endpoint is:

- Incidence of AEs including change from baseline in vital signs

The secondary endpoints are:

- Change from baseline in QHT (Day 4 QHT minus baseline QHT)
- QHT based on sub-scores from designated regions of the mouth (upper jaw, lower jaw, buccal and lingual surface)

7.2 Overall Study Design

This is a Phase 2, double-blind, two-armed, placebo-controlled, randomized, single-center, multiple dose study to evaluate the safety and proof of concept of KSL-W administered as a chewing gum formulation (APCG) 3 times per day over 4 treatment days. The study will evaluate the ability of APCG to reduce existing supragingival plaque. Plaque will be assessed using the QHT (Turesky et al-1970).

The OST and OHT will be examined. Changes from baseline, such as soft tissue erythema, ulceration and sloughing, will be noted and assessments will be made by the principal investigator or designee as to whether these events are related to treatment with APCG.

The study design is illustrated in [Table 3](#) and is detailed below. The Study Event Schedule is presented in [Table 4](#).

Table 3: Study Design

Treatment Day	Dosage* KSL-W / Placebo	# of Chews per Day**
Day 0	30 mg / 0 mg	3
Day 1	30 mg / 0 mg	3
Day 2	30 mg / 0 mg	3
Day 3	30 mg / 0 mg	3

* Subjects randomized to either KSL-W or placebo
**Each dose taken preferably after each meal (breakfast, lunch and dinner) or every 4-6 hours for a maximum of 3 chews per day

Table 4: Study Events Schedule

	Study Visit/Day					
	Visit 1	Visit 2				Visit 3
	Screening (-16 to -1)	Day 0	Day 1	Day 2	Day 3	Day 4
General Procedures						
Written Informed Consent/HIPAA	X					
Evaluation Inclusion/ Exclusion Criteria	X	X				
Demographic Data	X					
Medical History	X					
Vital Signs (BP, HR, RR Temperature)	X	X				X
Physical Exam	X					X ^a
Urine Drug Screen	X					
Urine Pregnancy Test	X ^b					X ^b
Periodontal Examination	X ^c					
Intraoral Exam (OHT, OST)	X	X				X
Oral Hygiene Check	X ^d	X ^d				X ^d
Randomization (1:1)		X				
Plaque Index Score	X	X ^e				X
Teeth Polishing		X				
Dispense Study Drug for Supervised and Unsupervised Use		X ^f				
Study Drug Administration		X ^g	X ^g	X ^g	X ^g	
Collect Used Study Drug		X ^h				X ^h
Electronic Diary Information System		X ⁱ	X ⁱ	X ⁱ	X ⁱ	
Adverse Event Reporting		X				X
Concomitant Medications	X	X				X
Study Discharge						X

BP-blood pressure, HIPAA=Health Insurance Portability and Accountability Act, HR-heart rate, RR-respiration rate, OHT-oral hard tissue, OST – oral soft tissue, QHT-Quigley-Hein Turesky Plaque Index

^a Brief symptom oriented physical exam (based upon reported adverse events)

^b Pregnancy test for females of childbearing potential

^c Includes determination of number of teeth, score-able surfaces and pocket depths around teeth

^d Confirm subject has refrained from all oral hygiene procedures (flossing, brushing of teeth, mouth wash rinse) for 12 to 16 hours prior to Screening and Day 0 (Baseline). On Day 4, confirm subject has refrained from all oral hygiene procedures since chewing their last dose on Day 3

[figure not shown]
^e Measured after randomization, but before teeth polishing

^f Subject will be allocated 14 tablets of gum for the 4 day study period

^g Subject will chew one tablet of gum for 20 minutes preferably after a meal (breakfast, lunch, dinner) or every 4 to 6 hours for a maximum of 3 chews per day. Chewing will be balanced as equally as possible between both sides of the mouth. The first tablet will be given under supervision in the clinic. Oral hygiene is not allowed at any time during the 4 day treatment. Oral hygiene cannot resume until after the determination of the Plaque Index Score on Day 4

^h After each chewing period, the gum is disposed of in individual labeled bags. Subject records time/date of gum disposal on each bag. Subject will return all used/unused bags to the site on Day 4.

ⁱ Subject records all start /stop times of gum chewing via the internet using the electronic diary information system (ePRO).

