- The first chew will be administered under supervision in the clinic. The subject will be instructed to chew one tablet of gum for 20 minutes. Chewing should be balanced as equally as possible between both sides of the mouth.
- After chewing the gum for the designated time, the subject will be given a used product bag to store the chewed gum. The evaluator will inform the subject to label this bag with the time and date of the chew.
- After the chewing gum is stored in the used product bag, the subject will complete the start and stop times for chewing gum on the electronic diary information system (ePRO). The subject will enter this information while in the clinic.
- The study drug will be dispensed for unsupervised use. The subject will receive:
 - 13 gum tablets for their unsupervised use along with 13 individual used product collection bags.
 - Subjects will be given instructions for chewing the gum.
 - a. The gum will be chewed for 20 minutes preferably after a meal or every 4 to 6 hours (3 times a day). Chewing will be balanced as equally as possible between both sides of the mouth for a maximum of 3 chews per day.
 - b. After completing each 20 minute chew, subjects will store the used gum in the used product collection bags provided to them.
 - c. Subjects will label each used product collection bag with the date and time of chew. (A separate bag will be used for each chew).
 - d. After each chew, subjects will record the start and stop time of the chew on the electronic diary information system - ePRO (Instructions provided in [Appendix D](#))
 - e. Subjects will be informed that they must bring all of the used product collection bags back to the clinic for Visit 3
- Subjects will be told that no oral hygiene procedures of any kind (teeth brushing, flossing or mouth wash rinse) will be allowed while on study treatment (Day 0, 1, 2, 3 and 4).
- AEs from first chew will be collected.
- Concomitant medication will be recorded.

9.1.3 Unsupervised Treatment, Study Days 0, 1, 2, and 3

After the first supervised chew is completed, the subjects will be released from the clinic. There will be a total of 11 unsupervised, self-administered chews. The subjects will chew one tablet of the gum (study drug) for 20 minutes every 4 to 6 hours, preferably after a meal, for a maximum of 3 chews per day according to the schedule in [Table 6](#).

Table 6: Schedule for Unsupervised Chews:

Time ^a	Day 0	Day 1	Day 2	Day 3
After Breakfast ^b	N/A	1	1	1

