After Lunch	1	1	1	1
After Dinner	1	1	1	1
Total Chews per Day	2	3	3	3

^a Gum will be chewed for 20 minutes preferably after a meal or every 4 to 6 hours for a maximum of 3 chews per day. Chewing will be balanced as equally as possible between both sides of the mouth.

^b First chew takes place in the clinic.

After completing each 20 minute chew, the subject will store the used gum in the used product collection bags provided to them. The subject will record the date and time of chew on the individual collection bags as instructed. A separate bag will be used for each chew. Subjects will record their chewing gum start and stop times on the electronic diary system (ePRO) after each chew.

9.1.4 Treatment, Study Day 4 – Visit 3

After 4 days of treatment, subjects will return to the clinic for Visit 3. The following procedures will occur at Visit 3:

- Subjects will return all used product bags and any unused product. Site Staff will collect used/unused product bags.
- Vital signs (diastolic and systolic blood pressures, heart rate, respiration rate and temperature) will be measured.
- A brief, symptom-oriented physical examination will be performed
- Females of child-bearing potential will take a urine pregnancy test
- Subjects will be asked to verify that he/she has refrained from all oral hygiene procedures (teeth brushing, flossing or mouth wash rinse) since their last chew.
- An intraoral exam (OST and OHT) will be performed.
- Supragingival plaque will be assessed using the QHT. (A red, food dye will be used to disclose plaque deposits on the teeth).
- AEs will be assessed.
- Concomitant medications will be recorded.

- Subject will be discharged from the study. (Subject will be allowed to brush their teeth just prior to leaving the research center is discharged from the study.)

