9.5 Procedures for Monitoring Subject Compliance

The first chew will be administered by the study staff and the chewing will be supervised at the clinic. Subject compliance will be monitored through supervision of the first dose, controlled distribution of product and collection of used product.

For unsupervised dosing, each subject will be provided with bags to collect the used product. Each bag will contain the used product of one chew. The bags (11 total) will be labeled to record product usage. Subjects will return the used product bags to the research center at Visit 3. Subjects will record the start and stop time of each chew on the electronic diary information system.

10 Proof of Concept Assessments

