12.8 Selection of Subjects to be Included in Analyses

The Full Analysis Set (FAS) is defined as all randomized subjects having Baseline and Day 4 QHT evaluations, with the Day 4 evaluation occurring on the morning following the last chewing gum treatment from the previous day. The FAS population will be analyzed according to their randomized treatment assignment.

The Per Protocol Population (PP) is a subset of FAS and consists of all subjects with no major protocol violations such as: failure to obtain valid informed consent, accidental distribution of incorrect study medication, not following the inclusion/exclusion criteria, evidence that study medication was not taken, and the performance of oral hygiene other than chewing the study gum during the study period. Analysis of the PP will be according to the treatment actually received by the subject.

The Safety Population consists of all randomized subjects receiving at least one dose of study medication, and summarized on the basis of treatment received. All AE summaries will be based on the safety population.

13 Direct Access to Source Data/Documents

Subjects will be identified on eCRFs by a unique subject identification number and on source documents by name and date of birth. No personal identifier will be used in any publication or communication used to support this research study. The subject identification number will be used if it becomes necessary to identify data specific to a single subject. Representatives of USAMRMC, the sponsor's representative, the IRB of Record and/or the USAMRMC ORP, and the FDA are eligible to review medical and research records related to this study as a part of their responsibility to protect human subjects in clinical research. Personal identifiers will be removed from photocopied medical and research records.

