15.1.3 Protocol Deviation Procedures

All subject-specific deviations from the protocol (eg, failure to return for follow-up visits) are to be documented. The Principal Investigator or designee will be responsible for identifying and reporting all deviations, which are defined as isolated occurrences involving a procedure that did not follow the study protocol or study-specific procedure. Deviations will be reported annually in the continuing review report to the IRB and/or the ORP and, if appropriate, in the final study report. Action taken in response to the deviation, and the impact of the deviation will be assessed by the Principal Investigator or sub-investigator and recorded as significant or nonsignificant.

Any protocol deviation that adversely affects the safety or rights of a subject or scientific integrity of the study, the deviation will be reported immediately to the sponsor's representative, IRB and/or the ORP.

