Appendix D. ePRO Electronic Diary Information

Each subject will record the start and stop times for chewing gum on the ePRO Electronic Diary Information System. This data will be collected via the internet. The subject will receive three emails per day containing a link to the respective ePRO form. Each form will be identified by "Day" and "Time of Chew". For example, for Day 1, the forms will be identified as: Day 1 – Chew 1 (morning), Day 1 – Chew 2 (afternoon), Day 1 Chew 3 (evening). Over the course of the study there will be a total of 12 forms (one for each chew) to be completed.

The subject will open the email and click the link to the ePRO form. On the form, the subject will enter the start and stop times for each chew and "submit" this information in real time.

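### The Day 4 oral hygiene check asks only about the time since the last Day 3 chew, but the ban and the Per Protocol exclusion cover the whole treatment period

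*Protocol*

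**What the plan says.** **The check.** Protocol Table 4, footnote d, instructs staff: "On Day 4, confirm subject has refrained from all oral hygiene procedures since chewing their last dose on Day 3". SAP Table 3, footnote d, repeats this. Protocol 9.1.4, which lists the Day 4 procedures, has the subject verify abstinence ("teeth brushing, flossing or mouth wash rinse) since their last chew").

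**The ban.** Footnote g of the same Protocol table says "Oral hygiene is not allowed at any time during the 4 day treatment". At Visit 2 (Protocol 9.1.2) subjects are told that no hygiene procedure "will be allowed while on study treatment (Day 0, 1, 2, 3 and 4"). The synopsis likewise runs the ban through all treatment days until after the Day 4 plaque assessment.

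**What the answer feeds.** Protocol 12.8 lists as a major violation, excluding a subject from PP, "the performance of oral hygiene other than chewing the study gum during the study period". SAP 6.1.1 and the TREF18 shell use the same period. The Day 4 column of LREF11 is headed as covering the time since the previous visit, glossed as all four treatment days.

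**Other monitoring.** Protocol 9.5 states: "Subject compliance will be monitored through supervision of the first dose, controlled distribution of product and collection of used product". It adds the chew-time diary, and Appendix D describes that diary's content: "Each subject will record the start and stop times for chewing gum on the ePRO Electronic Diary Information System". Neither mentions oral hygiene.

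**The concern.** The endpoint is plaque on Day 4 after polishing on Day 0, so brushing or rinsing in between directly changes what is measured. PP is the only analysis set meant to remove subjects who did this. Its membership depends on breaches being found, and the one scheduled question that could find them is written for a much shorter period than the rule it is meant to verify.

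A subject who brushed on Day 1, or on the afternoon of Day 3 before the dinner chew, could answer the written question truthfully and pass. That subject would stay in PP and be missing from the TREF18 hygiene count, and LREF11 would present an overnight answer as a four-day one. Agreement between FAS and PP could then be read as reassurance that it does not give.

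**Working it through.** The plan gives no figure to reproduce here. The check compares periods and then sizes the gap.

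**1. Periods side by side**

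| Item | Period covered |
|---|---|
| Day 4 check: Protocol Table 4 footnote d, Protocol 9.1.4, SAP Table 3 footnote d | last chew to Day 4 visit |
| Ban: Protocol synopsis, Table 4 footnote g, 9.1.2 | all treatment days, to the Day 4 plaque score |
| PP exclusion: Protocol 12.8, SAP 6.1.1 | study period |
| TREF18 deviation row | study period |
| LREF11 Day 4 column | since last visit, all four treatment days |

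The first sentence of footnote d, for Screening and Day 0, asks about exactly the 12 to 16 hours that its rule requires. Only the Day 4 sentence departs from its rule. Table 4 schedules no hygiene check on Days 1 to 3.

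**2. Share of the treatment period covered**

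- Chews (Protocol Table 6 plus the supervised one): 1 + (2 + 3 + 3 + 3) = 12.
- Intervals between chews: 12 − 1 = 11. The check covers none of them; it covers only the interval after chew 12.
- Hours: the documents give no clock times. Assume polishing and the Day 4 exam are both at about 09:00, so the period is 4 × 24 = 96 hours, and that the last chew ends between 18:00 and 22:00. The check then covers 15 to 11 hours: 15/96 = 15.6% down to 11/96 = 11.5%.

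**3. Effect of one misclassified subject on PP**

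- With 12 per arm, a subject whose change differs from the other subjects' by *x* QHT points moves the arm mean by *x*/12.
- *x* is not in the documents. Taking 0.5, 1.0 and 1.5 gives 0.042, 0.083 and 0.125.
- For scale, the standard error of the arm difference with the phase 2a SD of 0.22 (Protocol 12.2) is 0.22 × √(2/12) = 0.090. The plan itself assumes that these Day 14 results carry over to four days.
- The shift is therefore 0.042/0.090 = 0.47 to 0.125/0.090 = 1.39 standard errors.

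**4. Effect on FAS**

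FAS requires baseline and Day 4 QHT evaluations, with the Day 4 one on the morning after the last chew. The hygiene answer plays no part. The change in the FAS estimate, and in the forecast of future studies built on it (Protocol 12.1.2.1), is zero.

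**The case against.** The strongest counter-argument is that LREF11, the one item describing the recorded data, points to a four-day question. If the eCRF field asks about all four days, harm requires staff to ask less than the field in front of them. Subjects are told the full ban, listing LREF21.b records that they were reminded of it, and footnote g sits just below footnote d. A note in the TREF02 shell draws PP status from the protocol deviation record, and Protocol 15.1.3 requires that "All subject-specific deviations from the protocol (eg, failure to return for follow-up visits) are to be documented". The size calculation uses assumed clock times and an assumed QHT difference, and nothing indicates how many subjects would be affected. PP is supportive, and the p-values are descriptive.

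Much of this stands. The eCRF is not among the documents, so the consequence is conditional, and the stakes are limited to the PP results. The inconsistency remains. If the eCRF asks about four days, three passages misdescribe the check; if it asks only about the last night, LREF11 mislabels the answer. A reminder is not a check. The duty to document a deviation applies once a breach is known, so a deviation record still depends on a question that would bring the breach to light.

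**Conclusion.** The concern holds. The written Day 4 check covers a shorter period than the ban, the PP exclusion, TREF18 and LREF11, and no other scheduled question fills the gap. Followed as written, it can leave subjects in PP who should be excluded.

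The mismatch in the text is certain. Its effect is confined to PP membership, the TREF18 hygiene count and the FAS-versus-PP comparison. One misclassified subject would move a PP arm mean by about 0.04 to 0.13 QHT points, if that subject differs from the others by 0.5 to 1.5 points and the arm has 12 subjects. The documents give no basis for the number of such subjects. The FAS estimate does not change. This should be corrected, but it does not threaten the main proof-of-concept result.

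**What to change.** 1. Establish which period the eCRF question covers.
2. In Protocol Table 4 footnote d, Protocol 9.1.4 and SAP Table 3 footnote d, reword the Day 4 check to ask whether the subject has refrained from all oral hygiene since teeth polishing on Day 0. This matches the existing ban and LREF11 and adds no new clinical rule.
3. State in SAP 6.1.1 that this answer, with any other documented deviation, is used to assign PP status.
4. If Day 4 answers were already collected under the narrow wording, head the LREF11 column with the interval actually asked and state in the SAP that hygiene before the last chew was not checked. This may well apply: the SAP is dated 28 February 2017 and completion was estimated for August 2016. SAP section 8 already sends deviations from the SAP to the Statistical Analysis Report and Clinical Study Report.

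The cost is one sentence in three places, a line in the SAP, and no extra visit or procedure. A few more subjects may leave PP, and the check remains a retrospective self-report.

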7.3 Measures Taken to Minimize/Avoid Bias

7.3.1 Randomization

The random assignment of subjects to the 2 study arms will be 1:1. There will be 2 evaluators at the study site to assess the QHT scores, and the evaluator assigned to each subject will remain with that subject throughout the study. The randomization schedule will be generated by an independent biostatistician not involved in any way with the conduct and analysis of the study. The randomization schedule will be provided to designated study personnel for preparation of the blinded product and for emergency unblinding for safety reasons if necessary.

7.3.2 Blinding

For this double-blind study, the investigator, study biostatistician, staff not involved in product preparation and study subjects will be blinded to the treatment assignments throughout the duration of the study. A study specific procedure explaining the blinding and unblinding plan will be developed and maintained by appropriate study team members.

Salus Research will receive the investigational gum product directly from Fertin Pharma. Authorized product preparation staff at Salus Research will repackage the product into blinded individual opaque plastic vials in accordance with the randomization schedule. The product preparation staff will have no other responsibilities or involvement in the study. No other personnel are permitted in the preparation room during preparation of the blinded product.

The product preparation staff will receive a randomization schedule from the unblinded independent biostatistician. Each unique subject identification number will be assigned a treatment and this list will be used by the product preparation staff to prepare the blinded product. The blinded product will be labeled as shown in [Figure 1](#). Salus Research will be provided with individually sealed envelopes identifying each subject's specific treatment assignment. Salus Research will store these envelopes in a secure location accessible to the principal investigator in the event that the blind needs to be broken. The randomization, repackaging and labeling of the study product will be performed as per approved procedures in place at Salus Research.

Figure 1: Example Label for Blinded Product Vials

Subject ID Number:

Directions for Subject: Chew 1 tablet for 20 minutes balanced equally on both sides of the mouth. Each dose should be taken preferably after each meal (breakfast, lunch and dinner) or every 4-6 hours for a maximum of 3 chews per day.

Storage Instructions: Material to be stored at ambient room temperature, out of direct sunlight. Do not expose to extreme heat or cold.

Caution: New Drug – Limited by Federal (or U.S) law for investigational use.

Distributed by: Salus Research

Phenylketonurics: Contains Phenylalanine

KEEP OUT OF REACH OF CHILDREN

[name], Principal Investigator Study S-16-10

Emergency [contact]

Non-emergency [contact]

7.3.3 Unblinding

Emergency unblinding of a subject should only be done in the case of a medical emergency, or in the event of a serious medical condition, when knowledge of the investigational study product is essential for the clinical management or welfare of the subject. In such an emergency situation, the Principal Investigator may unblind a subject's treatment without first discussing with the Sponsor's Safety Physician. While it is recommended to discuss with the Sponsor's safety physician prior to unblinding, the safety of the subject is the highest priority. The Sponsor will be notified by the Principal Investigator when emergency unblinding has occurred. Only the Principal Investigator or Sponsor can authorize emergency unblinding. The reason for unblinding should be clearly specified in the source documentation.

The individual treatment codes for each subject will be given to Salus Research in sealed envelopes. Each individual envelope will contain the subject identification number and their specific treatment assignment. These envelopes will be stored in a secure location accessible to the Principal Investigator in the event that the blind needs to be broken for emergency unblinding or individual emergency safety unblinding.

Contact Information for Emergency Unblinding:

Responsible person:

- Salus Research: [name],
[contact]
- Army: [name] Acting-Director, Clinical Services Support Division
[contact]

